## **2.3 Risk/Benefit Assessment**

### **2.3.1 Known Potential Risks**

Risks include those associated with: a) clinical rating scales and psychiatric assessment; b) MRI; c) EKG, d) placement of venous and arterial lines; e) arterial blood sampling; f) radiation exposure from the radioligand and from the transmission scan; g) PET scanning.

#### **2.3.1.1 Risks of Clinical Rating Scales and Psychiatric Assessment**

No discomfort is expected to occur during clinical interviews or psychological assessments, other than the potential emotional stress caused by discussing difficult psychiatric topics.

#### **2.3.1.2 MRI**

People are at risk for injury from the MRI magnet if they have pacemakers or other implanted electrical devices, brain stimulators, some types of dental implants, aneurysm clips (metal clips on the wall of a large artery), metallic prostheses (including metal pins and rods, heart valves, and cochlear implants), permanent eyeliner, an implanted delivery pump, or shrapnel fragments. Welders and metal workers are also at risk for injury because of possible small metal fragments in the eye of which they may be unaware. Participants will be screened again for these conditions before having any scan and will not receive an MRI scan if they have any contraindications.

It is not known whether MRI is completely safe for a developing fetus. Therefore, all women of childbearing potential will have a urine pregnancy test performed no more than 24 hours before each MRI scan. The scan will not be done if the pregnancy test is positive.

People with fear of confined spaces may become anxious during an MRI. Those with back problems may have back pain or discomfort from lying in the scanner. The noise from the scanner is loud enough to damage hearing, especially in people who already have hearing loss. Everyone having a research MRI scan will be fitted with hearing protection. Participants will be asked to complete an MRI screening form for each MRI scan they have. There are no known long-term risks associated with MRI scans.

#### **2.3.1.3 EKG**

The patient may feel uncomfortable while the electrodes are attached to the chest. The conductive gel sometimes causes some mild irritation.

#### **2.3.1.4 Placement of Venous and/or Arterial Line**

Venous catheter insertion can be associated with discomfort, bruising, infection, or clot formation. Using proper placement techniques will minimize these risks. In case of tracer extravasation, we will stop the study, remove the venous line from the arm, and apply cold to the site. Arterial catheterization is a generally safe and reliable method of obtaining arterial blood samples [28, 29]. Placement of a radial arterial catheter may cause bruising or infection. There is also a risk of occlusion and microemboli. Over 3,000 arterial catheters have been placed to date in the PET Department. Of these, only two complications requiring physician's care arose. In the first case, a small radial artery aneurysm developed several months later, which was successfully

repaired surgically. In the second case, a radial artery thrombosis developed 28 days later, which was also successfully repaired surgically.

### **2.3.1.5 Blood Sampling**

Participants may have arterial or venous blood sampling. The total amount of blood drawn shall not exceed 10.5 mL/kg or 550 mL, whichever is smaller, over any eight-week period. Blood sampling may lead to the formation of small subcutaneous hematomas caused by blood leaking from a punctured blood vessel. Such hematomas cause only minor discomfort. They are not dangerous and require no treatment other than reassuring the participant. There is also a small risk of infection at the site of the needle puncture, which can be readily treated with antibiotic therapy. We will ask participants not to donate blood within eight weeks before the study and for eight weeks following the study.

### **2.3.1.6 Radiation Exposure Risks**

Radiation exposure in this protocol will be from  $[^{11}\text{C}](R)$ -rolipram and the associated transmission scans.

The radiation exposure (rem) from two injections of  $[^{11}\text{C}](R)$ -rolipram, 20 mCi each, which is a typical dose for brain imaging, is: effective dose (0.8). Gallbladder (1.6), lungs (2.2), and liver (1.9) are the three organs with the highest levels [30].

With regard to exposure from the transmission scan, the PET Department recently implemented [name] suggestion to decrease the current (amperage) and, thus, overall radiation from the CT scan. We do not need a high resolution (high current) image for attenuation correction; a low-resolution scan, like that obtained from a line source, is perfectly adequate to correct attenuation in the PET emission scan. With the lowered current, the exposure to the lens of the eye is now 0.26 rem, about one-third of the previous value.

We routinely include the dose from two transmission scans for each PET scan in the event that it must be repeated in any given participant. Therefore, four CT scans might be necessary. The effective dose for four head transmission scans from a PET/CT is  $\sim 0.08$  rem. Thus, the maximum total effective dose in each  $[^{11}\text{C}](R)$ -rolipram PET scan is 0.44 rem, and for the whole study it would be 0.88 rem. These estimated annual effective doses are well below the limit of 5 rem per year established by the NIH's Radiation Safety Committee. All participants will be asked about any prior research participation involving radiation exposure so that the total exposure, in combination with the present study, will not exceed an effective dose of 5 rem per year.

### **2.3.1.7 PET Scan**

PET scans, which detect injected radioactivity within the body, are not associated with any known physical hazards to the participant lying on the table. We routinely use a series of procedures to minimize the risk of discomfort during scanning sessions. The procedures are conducted in the presence of trained health professionals to whom participants will have ready access should they experience any problems. Participants can communicate with the trained health professionals while in the scanner and can be removed from the scanner and withdraw from the study at any time if they wish to do so. Participants can also request that the operator stop the scan.

### 2.3.2 Known Potential Benefits

This study offers no direct benefits to the participants related to the PET scans but will likely provide fundamental knowledge regarding the mechanism of action of ketamine in the treatment of depression.

### 2.3.3 Assessment of Potential Risks and Benefits

If the results are positive, PET imaging with [C](R)-rolipram may be used to explore the pathophysiological role of cAMP in depression as well as shed light on the mechanism of action of ketamine. This valuable information may then help guide future trials with anti-depressant drugs, a benefit to future patients that justifies the risks to the current participants.

With regard to how the study design sought to minimize risks, please see each risk listed above (Section 2.3).

## 3 OBJECTIVES AND ENDPOINTS

Objectives	Endpoints	Justification for Endpoints
Primary		
Measurement of cAMP signaling via [  C](R)-rolipram density (distribution volume $V_T$ ) in the brains of individuals with MDD before and after ketamine infusion	Distribution volume $V_T$ of [  C](R)-rolipram pre- and post-ketamine scan	Change in $V_T$ of [  C](R)-rolipram is a surrogate marker for cAMP signaling, a proposed mechanism for ketamine's mechanism of action
Secondary/Exploratory		
1) The relationship between clinical rating scales and PDE4B binding	1) Distribution volume $V_T$ 2) Clinical rating scales	Correlation between $V_T$ and clinical ratings

## 4 STUDY DESIGN

### 4.1 Overall Design

- **Site:** This single-site study will be conducted at the NIH Clinical Center.
- **Hypothesis:** We hypothesize that PDE4 levels as quantified by [C](R)-rolipram in the brains of subjects suffering from a major depressive episode will be increased with ketamine administration, and that these levels will correlate with clinical rating scales.
- **Type of Design:** MDD participants will be studied with [C](R)-rolipram prior to and after ketamine infusion.

- **Study Groups:** Individuals with MDD
- **Study intervention:** Two PET scans with [C](R)-rolipram and MRI of brain.
- **Interim Analysis:** None.
- **Stratifications:** None.

#### 4.2 Scientific Rationale for Study Design

This study is exploratory and seeks to gather information that would be useful for designing a larger follow-up study.

#### 4.3 Justification for Dose

Previous studies with [C](R)-rolipram used a dose of 20 mCi, which is enough to measure both radioactivity in brain with PET and the concentration of parent radioligand in arterial plasma.

### 5 STUDY POPULATION

#### 5.1 Inclusion Criteria

**Patients:** In order to be eligible for this study, MDD participants must meet all of the following criteria:

1. Aged 18 to 70 years old.
2. Female participants of childbearing potential must be using a medically acceptable means of contraception.
3. Participants must be in good general health as evidenced by medical history and physical examination.
4. Each participant must have a level of understanding sufficient to agree to all required tests and examinations and sign an informed consent document.
5. All participants must have undergone a screening assessment under protocol 01-M-0254, “The Evaluation of Patients with Mood and Anxiety Disorders and Healthy Participants”.
6. Participants must be enrolled in the ketamine arms of protocols 19-M-0107 “Ketamine and AMPA”, 17-M-0060 “Neuropharmacology of Ketamine”, or 15-M-0188 “Neurobiology of Suicide”.
7. Participants must fulfill DSM-5 criteria for major depression (MDD) without psychotic features, as based on clinical assessment and structured diagnostic interview (SCID-P).
8. Participants must have an initial score on the MADRS  $\geq 18$  or HAM-D  $\geq 15$  within two weeks of study entry.
9. Participants with stable medical conditions as assessed by their primary care provider (PCP) and/or in-house clinician are permitted to join the study.
10. Patients must qualify for ketamine administration, usually defined as lack of response to two adequate lifetime antidepressant trials, with [at least] one in the current major depressive episode, operationally defined using the Antidepressant Treatment History Form (ATHF); a failed adequate trial of ECT [or TMS] would count as an adequate antidepressant trial.
11. Participants must have their radial artery pulse checked for the presence of adequate ulnar collateral flow and the absence of any metal or foreign objects in both wrists.
12. Participants must agree to adhere to the lifestyle considerations (see Section 5.4).

## 5.2 Exclusion Criteria

Participants with MDD who meet any of the following criteria will be excluded from participation in this study:

1. Clinically significant abnormalities on EKG or laboratory testing. This includes CBC, acute care panel (Na, K, Cl, CO2, creatinine, glucose, urea nitrogen); prothrombin and partial prothrombin tests, the PT/PTT is optional for those without history of coagulation disorders or those not on anticoagulation.
2. Current psychotic features, a diagnosis of schizophrenia or any other psychotic disorder as defined in the DSM-5.
3. Participants with a history of DSM-5 substance use disorder (except for caffeine or nicotine dependence) within the preceding three months. In addition, participants must not have substance use disorder or alcohol use disorder. However, alcohol or cannabis use by themselves are not exclusion criteria, unless that use affects the function of daily life.
4. Participants who, in the investigator's judgment, pose a current serious suicidal or homicidal risk.
5. Participants who have a history of aggressive behavior towards others.
6. Participants who have an unstable medical condition that, in the opinion of the investigators, makes participation unsafe (e.g., an active infection or untreated malignancy).
7. Are unable to travel to the NIH.
8. Have recent exposure to radiation related to research (e.g., PET from other research) that, when combined with this study, would be above the allowable limits.
9. Have an inability to lie flat and/or lie still on the camera bed for at least two hours, including claustrophobia, overweight greater than the maximum for the scanner, and uncontrollable behavioral symptoms, which will be screened by an interview with the participant during the screening visit.
10. Are unable to have an MRI scan (e.g., because of pacemakers or other implanted electrical devices, brain stimulators, dental implants, aneurysm clips (metal clips on the wall of a large artery), metallic prostheses (including metal pins and rods, heart valves, and cochlear implants), permanent eyeliner, implanted delivery pumps, shrapnel fragments, or metal fragments in the eye).
11. Be NIMH staff or an NIH employee who is a subordinate/relative/co-worker of the investigators.
12. Pregnancy
13. HIV infection

### 5.2.1 Exclusion of Children

Because this protocol has more than minimal risk from radiation exposure without possibility of direct benefit, inclusion of children is not appropriate.

### **5.2.2 Exclusion of Pregnant or Breastfeeding Women**

Pregnant women will be excluded because this protocol involves exposure to ionizing radiation. Lactating women will be excluded because radioisotopes may be excreted in milk.

### **5.2.3 Exclusion of Participants who are HIV Positive**

Persons with HIV infection are excluded because HIV infection itself may change cAMP signaling.

## **5.3 Inclusion of Vulnerable Participants**

### **5.3.1 Safeguards for Vulnerable Populations and Sensitive Procedures**

#### **5.3.1.1 Role of the HSPU**

The Human Subjects Protection Unit will monitor the consent process for all MDD participants.

#### **5.3.2 Participation of NIH Staff or family members of study team members**

NIH staff may be enrolled in this study as the population meets the study entry criteria and NIH Policy 404 will be followed. There will be no direct solicitation of NIH employees, nor will they be directly recruited by or through their supervisors or co-workers to participate in this study. Neither participation nor refusal to participate as a subject in the research will have an effect, either beneficial or adverse, on the participant's employment or position at NIH. NIH employees must have permission from their supervisor and/or take leave in order to receive compensation if participation is during work hours. Prior to enrollment, the NIH employee will be requested to review the Annual Leave Policy for NIH Employees. Participant confidentiality and privacy will strictly be held in trust by the participating investigators, their staff, and the sponsor(s).

Per NIMH Policy, NIMH employees, staff and their immediate family members will be excluded from the study due to ethical concerns about confidentiality and conflict of interest. A copy of the NIH Frequently Asked Questions (FAQs) for Staff Who are Considering Participation in NIH Research ) will be made available for NIH employees who wish to participate in this study.

This study collects sensitive medical information. Every effort will be made to protect participant information, but such information may be available in medical records and may be available to authorized users outside of the study team in both an identifiable and unidentifiable manner. The PI will train study staff regarding obtaining and handling potentially sensitive and private information about co-workers through staff discussions.

## **5.4 Lifestyle Considerations**

During this study, participants will be asked to abstain from strenuous exercise and from lifting more than 10 pounds using the affected arm for 48 hours after removal of the arterial line. Patients will be asked not to donate blood for 8 weeks before or 8 weeks after PET scans.

## 5.5 Screen Failures

Screen failures are defined as participants who consent/assent to participate in the clinical trial but are not subsequently assigned to the study intervention or entered in the study. A minimal set of screen failure information is required to ensure transparent reporting of screen failure participants, to meet the Consolidated Standards of Reporting Trials (CONSORT) publishing requirements, and to respond to queries from regulatory authorities. Minimal information includes demographic characteristics, screen failure details, eligibility criteria, and any serious adverse event (SAE).

Individuals who do not meet the criteria for participation in this trial (screen failure) because of an exclusion criterion that may resolve by the time of treatment may be rescreened. Rescreened participants should be assigned the same participant number as for the initial screening.

## 5.6 Strategies for Recruitment and Retention

Participants will be recruited from protocol #'s 19-M-0107 "Ketamine and AMPA", 17-M-0060 "Neuropharmacology of Ketamine" or 15-M-0188 "Neurobiology of Suicide."

The protocol and contact information to obtain further details will be listed on [www.clinicaltrials.gov](http://www.clinicaltrials.gov).

### 5.6.1 Costs

We expect participants to incur no costs for participating in this study.

### 5.6.2 Compensation

Participants will be compensated for time- and research-related inconveniences. Reimbursement is based on NIH standards for time devoted to the research project. Participants will be paid for each portion of the study they complete whether or not they opt for early withdrawal from participation. Without any delay of study procedures or unanticipated inconvenience, the total possible compensation for procedures is \$730. Participants will also receive compensation for time spent at each visit following the structure of \$20 for the first hour and \$10 for each subsequent hour. If the investigators need to delay study procedures or if additional time is need for completion, participants may receive additional compensation in accordance with NIH guidelines.

Participants may receive support for travel, meals, and lodging according to NIH travel policy guidelines. Lodging may be provided directly or reimbursed according to NIH guidelines. For NIH employees, guidelines per Policy 404 will be followed. Employees and staff who participate during work hours must have permission from their supervisor. NIH employees must either participate outside of work hours or take leave in order to receive compensation.

Visit 1 to NIH	
Screening	\$50
Pregnancy test	\$10
Psychiatric evaluation	\$50
Visit 2 to NIH	

*Abbreviated Title: cAMP Signaling Affected by Ketamine*

*Version Date: 09/11/23*

PET scanning	\$150
Arterial catheter	\$60
Antecubital venous catheters	\$30
Pregnancy test	\$10
Movement restriction	\$10
Visit to NIH 3 *	N/A
Visit 4 to NIH	
PET scanning	\$150
Arterial catheter	\$60
Antecubital venous catheters	\$30
Pregnancy test	\$10
Movement restriction	\$10
Visit 5 to NIH	
MRI	\$100
Total	\$730

\*Ketamine infusions will be performed under protocols #19-M-0107 “Ketamine and AMPA”, 17-M-0060 “Neuropharmacology of Ketamine” or 15-M-0188 “Neurobiology of Suicide

## 6 STUDY INTERVENTION

### 6.1 Study Interventions(s) Administration

#### 6.1.1 Study Intervention Description

Each participant will receive two injections of [C](R)-rolipram, prior to and after ketamine infusion, and will also receive an MRI.

#### 6.1.2 Dosing and Administration

Each participant will be intravenously injected with about 20 mCi of [C](R)-rolipram for each PET scan. The yield of the radioligand synthesis varies such that the available dose may be more or less than 20 mCi. By prior agreement with NIH’s Radiation Safety Committee, the clinician covering the scan can approve a dose as low as half of the prescribed dose. We expect that a dose of about 20 mCi will likely be adequate for all participants per scan. The maximal dose will provide the best accuracy to measure radioactivity in brain with PET and the parent radioligand in plasma with radioHPLC.

##### 6.1.2.1 Dose Escalation

None.

##### 6.1.2.2 Dose Limiting Toxicity

Toxicity from this radiolabeled drug comes from radioactive emissions and the mass dose of the nonradioactive carrier. Both the injected radioactivity and mass dose are many-fold lower than that required to cause toxicity.

*Abbreviated Title: cAMP Signaling Affected by Ketamine*  
*Version Date: 09/11/23*

#### **6.1.2.3 Dose Modifications**

The dose will not be modified by toxicity. Instead, the dose may be less than that prescribed, based on the PI's judgment of the magnitude of noise that will be acceptable in the brain and blood measurements.

#### **6.1.2.4 Drug Administration**

The radioligand will be injected intravenously.

### **6.2 Preparation/Handling/Storage/Accountability**

[figure not shown]
The radioligands are prepared by the NIMH radiochemistry laboratory and handled by the PET Department radiopharmacy according to the associated INDs and SOPs. The radioligands have minimal storage because they must be injected within one hour of their preparation.

#### **6.2.1 Acquisition and Accountability**

[figure not shown]
The radioligand will be delivered by the NIMH radiochemistry laboratory to the PET Department's radiopharmacy. Acquisition and accountability are the responsibility of the NIMH radiochemistry laboratory.

#### **6.2.2 Formulation, Appearance, Packaging, and Labeling**

Each product will be formulated in sterile, apyrogenic saline containing 10% dehydrated alcohol in a single-use vial and labeled according to requirements for PET drug products described in USP Chapter <823>. The following label will be affixed directly to the vials prior to filling:

Two additional labels are placed on the outer lead shielding used to transport the vial to the radiopharmacy:

C(R)-Rolipram Injection	
Batch #: ROL-	Activity: _____ mCi
Calibration Date:	EOS Time:
Sterile, apyrogenic saline solution for i.v. administration (contains 10% dehydrated alcohol)	
Half-life of  C is 20.4 min	
Expiration Time: _____	

### **6.2.3 Product Storage and Stability**

Products are stable at controlled room temperature for the one-hour expiration period and have no additional storage requirements. Product vials are expected to be single-use, but if the seal is broken and additional product must later be withdrawn, the same storage conditions and original expiration time would apply.

### **6.2.4 Preparation**

Products are provided as sterile, directly injectable solution in a multi-dose vial. The PET radiopharmacist will aseptically remove from the multi-dose vial only the volume required for a participant dose. If necessary, this volume will be diluted with 0.9% normal saline, USP to 12 mL

### **6.3 Measures to Minimize Bias: Randomization and Blinding**

This study is neither randomized nor blinded.

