### **8.2.3 Biospecimen Evaluations**

After injection of the radioligand, arterial sampling will be performed continuously at early time points and discretely at later time points, but this plan can be modified if required to improve quality of data. Participants may have arterial or venous blood sampling. The total amount of blood drawn shall not exceed 10.5 mL/kg or 550 mL, whichever is smaller, over any eight-week period.

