## 9 STATISTICAL CONSIDERATIONS

### 9.1 Statistical Hypothesis

- Primary Endpoint(s):  $V_T$  of  $[^{11}\text{C}](R)$ -rolipram prior to ketamine infusion compared to  $V_T$  of  $[^{11}\text{C}](R)$ -rolipram after ketamine infusion, within one week. We hypothesize that ketamine infusion will increase rolipram binding similar to that previously described for SSRI treatment.
- Secondary Endpoint(s): We will explore correlations between changes in  $[^{11}\text{C}](R)$ -rolipram binding and clinical rating scales.

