### 9.2 Sample Size Determination

The only existing database of patients scanned for PDE4 at baseline and after treatment is the one described by Fujita et al. This work, whose patients were very similar to the ones targeted in this study, analyzed 23 MDD subjects with  $^{11}\text{C}$ -rolipram at baseline and after 8 weeks of antidepressant SSRI treatment. MDD subjects had a ~20% reduction in rolipram binding compared to controls, and the SSRI treatment significantly increased  $^{11}\text{C}$ -rolipram binding by 12% ( $P<0.001$ ). Consequently, we aim at studying a population of the same size as the one that revealed a significant change with pharmacological treatment. Considering dropouts, we wish to recruit up to 35 subjects, with the goal of scanning 23. Correlation/regression analyses will be performed by controlling for possible confounding factors such as age and sex.

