#### **9.4.2 Analysis of the Primary Endpoints**

[C](R)-rolipram binding assessed as VT will be compared within subjects with a paired sample *t*-test. VT will be calculated using pharmacokinetic modeling.

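### No masking of scan order is planned for the PET processing that yields V_T, in a single-group pre/post comparison with an increase predicted in advance

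*Combined protocol and SAP*

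**What the plan says.** Section 6.3 of the combined protocol and SAP consists of one sentence: "This study is neither randomized nor blinded". Section 6.4 repeats it under intervention compliance. Neither section mentions image analysis.

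Section 4.1 gives a single study group, "Individuals with MDD", scanned before and after ketamine. Section 9.1 states the expected direction: "We hypothesize that ketamine infusion will increase rolipram binding similar to that previously described for SSRI treatment". Under section 9.4.2, V_T "will be compared within subjects with a paired sample" t-test, and V_T "will be calculated using pharmacokinetic modeling". That section names no kinetic model, region set, input-function fitting rule or scan-exclusion rule.

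The PET procedures (8.2.1), the biospecimen and plasma sections (8.2.3 and 8.2.4) and the statistical chapter (9.1 to 9.4) contain no coding of scans, no masking to scan order or rating scores, and no lock of the V_T values before the comparison. Section 4.2 describes the study as exploratory and meant to inform a larger one.

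**The concern.** Ketamine is given openly under other protocols, and nothing in this study could mask it. The offline work is different. Region definition, input-function fitting and V_T estimation take place after the scan and can be done on coded files. The plan does not use that option.

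The omission matters because of the design. The paired t-test asks whether the mean post-minus-pre difference is zero. With no control group, a processing choice that falls slightly differently on second scans than on first scans is not subtracted out. It becomes part of the ketamine effect, and the team has already stated which direction it expects. Section 9.4.1 also correlates the modeling results with the clinical scales, and nothing keeps those scores from whoever produces V_T. At stake is how far the primary estimate can be trusted, including as an input to the larger study.

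**Working it through.** **The plan's own figure.** Section 9.2 sets 23 scanned participants by copying the size of the earlier SSRI study. It states no alpha, power or SD, so there is no formula to reproduce. Masking does not alter the number.

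**Inputs**
- n = 23 pairs (section 9.2).
- Earlier result: a 12% increase with P<0.001 in 23 patients (sections 2.2 and 9.2).
- Two-sided alpha of 0.05: assumed.
- Systematic post-minus-pre processing shift b of 1, 2, 3 or 5 percentage points: assumed, because the documents give none.

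**Step 1: a bound on the SD of change.** Suppose the earlier P value came from a two-sided paired t-test on percent change; the documents do not name the test. Then t was at least t(0.9995, df 22) = 3.792.
- SE ≤ 12 / 3.792 = 3.16
- SD ≤ 3.16 × √23 = 3.16 × 4.796 = 15.2%

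An SD of 10% is added as an assumed smaller value. An SD of 20% covers the case where the supposition fails.

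**Step 2: false-positive rate when the true change is zero but V_T carries a shift b.** The t statistic is then noncentral t with 22 df and noncentrality δ = b × √23 / SD. The test rejects when |T| > t(0.975, 22) = 2.074. For example, b = 3 and SD = 15.2% give δ = 3 × 4.796 / 15.2 = 0.95 and a rejection probability of 0.148.

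| Assumed shift (points) | SD 10% | SD 15.2% | SD 20% |
|---|---|---|---|
| 0 | 5% | 5% | 5% |
| 1 | 7% | 6% | 6% |
| 2 | 15% | 9% | 7% |
| 3 | 28% | 15% | 11% |
| 5 | 63% | 33% | 21% |

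**Step 3: scale.** The smallest observed mean change that reaches significance is 2.074 × SD / √23: 4.3% at SD 10% and 6.6% at SD 15.2%. A 3-point shift is a quarter of the 12% effect seen with SSRI treatment (3/12) and a little under half of the 6.6% threshold. A 1-point shift leaves the error rate close to nominal.

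**The case against.** The best defence is that V_T is not a reader's score. It is a quantitative estimate that uses measured parent radioligand in arterial plasma (8.2.1 and 8.2.4). One brain MRI per participant supplies the anatomy for both scans (1.2 and 8.2), which limits how far region placement can differ by order. The study is openly exploratory (4.2). These points stand, and they reduce the room for bias. They do not remove it, because model choice, input-function fitting and exclusions are not fixed in advance.

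Some stronger readings are tempting, and the documents do not support them:
- **That analysts know which scan is which.** The plan does not say so. Section 6.3 names no analyst and no analysis step. What can be said is that no masking is planned.
- **That the false-positive figures predict bias.** No document gives a shift. Five points would be over 40% of the SSRI effect (5/12 = 42%) and would have to come from processing alone.
- **That the freedom to change arterial sampling adds to the case.** Section 8.2.3 allows that "this plan can be modified if required to improve quality of data", but this is a scan-day decision, and coding the files afterwards cannot mask it.
- **That testing several regions adds to the case.** Error from multiple regions would be the same for a masked analyst. It is a separate prespecification matter.
- **That the secondary correlation is biased.** This is possible but unquantified. Section 8.2.2 also lets post-ketamine ratings be done by another branch's staff under their own protocols.

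**Conclusion.** The point holds as a missing safeguard. The plan provides no masking of scan order for the processing behind its primary endpoint, in a design where any order-dependent shift adds fully to the estimate. It does not show that bias will occur or how large it would be.

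The size is a sensitivity range. For assumed shifts of 1 to 5 points, the two-sided error rate runs from 6% to 33% at SD 15.2% and from 7% to 63% at SD 10%. This rests on the assumed alpha and shift and, for the 15.2% bound, on the test assumed for the earlier study. The plan should be changed because the safeguard is simple. The study can run without it, but its primary result would be less credible.

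**What to change.** Amend section 6.3 to say:
- Ketamine is open-label, but PET scans and arterial data are coded by existing staff after acquisition.
- Region definition, input-function fitting and V_T estimation are done without scan date, pre/post order or rating scores.
- The same kinetic model, regions and scan duration are used for both scans of a participant.
- The V_T file is locked before the code is broken.

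The cost is protocol wording, a file-coding step and a short delay before results can be viewed. A staff member other than the analyst must hold the code. The documents do not describe analysis staffing or costs, so calling this cheap is a judgment. Visits, participant procedures and the targets of 23 scanned and up to 35 recruited are unchanged.

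Scan-day staff stay unmasked. Time, test-retest and regression effects also remain, because only a control group would address them.
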